10.17. Appendix 17: Protocol Amendment History

This is the first amendment to the original protocol.

1. INTRODUCTION

This statistical analysis plan (SAP) contains definitions of analysis sets, derived variables, and statistical methods for the analysis of efficacy, safety, pharmacokinetics (PK), pharmacodynamics (PD), Immunogenicity and health-related quality of life in the CNT01959HDS2001 study.

1.1. Trial Objectives

Primary Objective

The primary objective of this study is to evaluate the initial efficacy, safety, and tolerability of guselkumab in adult participants with moderate to severe hidradenitis suppurativa (HS).

Secondary Objectives

The secondary objectives of this study are:

- To evaluate the efficacy of guselkumab in adult participants with moderate to severe HS during the maintenance phase.
- To evaluate the effect of guselkumab on the dermatologic health-related quality of life in adult participants with moderate to severe HS.
- To evaluate the pharmacokinetics (PK), immunogenicity, and pharmacodynamics (PD) of guselkumab therapy in adult participants with moderate to severe HS.

1.2. Trial Design

This is a Phase 2, multicenter, randomized, placebo-controlled, double-blind, proof-of-concept (POC) study evaluating the efficacy, safety, PK, and immunogenicity of SC and IV administered guselkumab for the treatment of moderate to severe HS in adult participants. The participant population will comprise men and women who have had moderate to severe HS for at least 1 year.

A diagram of the study design ([Figure 1](#)) is provided below and as depicted in [Figure 1](#), approximately 180 participants who satisfy all inclusion and exclusion criteria will be randomized in a 1:1:1 ratio to 1 of 3 groups:

Group 1: Guselkumab Regimen 1 (1200 mg IV q4w x 3 → 200 mg SC q4w)

Participants will receive guselkumab 1200 mg IV at Week 0, Week 4, and Week 8 (ie, a total of 3 IV guselkumab doses and 3 SC placebo doses). At Week 12, participants will continue treatment with guselkumab 200 mg SC q4w through Week 36.

Group 2: Guselkumab Regimen 2 (200 mg SC q4w x 3 → 200 mg SC q4w)

Participants will receive guselkumab 200 mg SC at Week 0, Week 4, and Week 8 (ie, a total of 3 SC guselkumab doses and 3 IV placebo doses). At Week 12, participants will switch treatment to guselkumab 200 mg SC q4w through Week 36.

Group 3: Placebo

[figure not shown]
Participants will receive placebo IV and SC at Week 0, Week 4, and Week 8 (ie, a total of 3 IV and 3 SC placebo doses) and an additional SC placebo dose at Week 12. At Week 16, participants will be rerandomized in a 1:1 ratio to either guselkumab 200 mg SC q4w through Week 36 or guselkumab 100 mg SC at Weeks 16, 20, 28, and 36, and placebo at Weeks 24 and 32.

A screening period will take approximately 4 weeks. All participants will enter safety follow-up after Week 36 through Week 48. Two planned database locks (DBLs) will occur, at Week 16 and at Week 48.

Efficacy assessments (HS-IGA, lesion counts, Hurley staging, Hidradenitis Suppurativa Symptom Diary [HSSD], Dermatology Life Quality Index [DLQI], Hospital Anxiety and Depression Scale [HADS], and Patient's Global Impression of Change [PGIC]) will be performed according to the Schedules of Activities. Serum samples for PK, immunogenicity, and biomarker analyses will be collected at the timepoints shown in the Schedules of Activities (Section 1.3 of the protocol).

An interim analysis is planned. A sponsor's committee, otherwise not involved in the study conduct, will be responsible for reviewing the results of this interim analysis. In addition, a separate, external independent DMC will be commissioned for this study for safety evaluation. Refer to Section 9.5 of the protocol (Interim Analysis) and Section 9.6 of the protocol (Data Monitoring Committee) for details.

Figure 1: Schematic Overview of CNTO1959HDS2001

1.3. Statistical Hypotheses for Trial Objectives

The primary hypothesis is that guselkumab treatment is superior to placebo as assessed by the proportion of participants achieving Hidradenitis Suppurativa Clinical Response (HiSCR) at Week 16.

- HiSCR is defined as at least 50% reduction in total abscess and inflammatory nodule count (AN count) with no increase in abscess count and no increase in draining fistula count relative to baseline.

The major secondary hypotheses are that guselkumab treatment is:

- Superior to placebo as assessed by the change from baseline in AN count at Week 16.
- Superior to placebo as assessed by the improvement in patient-reported outcomes (PRO) as measured by:
 - The change from baseline in DLQI score at Week 16.
 - The change from baseline in HS-related pain in the past 24 hours based on HSSD at Week 16.

1.4. Sample Size Justification

This study is designed to enroll approximately 180 participants in order to have sufficient power to detect a difference between the guselkumab groups and the placebo group for the primary efficacy endpoint. The rationale for the study sample size is based on the hypothesis tests for the primary efficacy endpoint.

Two adalimumab (Humira®) Phase 3 clinical studies have been conducted to evaluate the safety and efficacy of adalimumab in the treatment of adult participants with moderate to severe HS. The response rates observed in Study M11-313 (PIONEER I) and M11-810 (PIONEER II) for HiSCR at Week 12 were 42% vs 26% and 59% vs 28% in the adalimumab weekly group and placebo group, respectively.

Therefore, based on the data from these studies, various assumptions to calculate sample size and power are shown in [Table 1](#).

Based on these assumptions, with 60 participants in each of the guselkumab treatment group and 60 participants in the placebo group, there will be more than 80% power to detect a treatment difference with a 2-sided significance level of 0.05.

	Treatment group	Sample size	HiSCR	Δ (difference)	Power
1	Placebo	60	20%	25%	85%
	Guselkumab	60	45%		
2	Placebo	60	20%	30%	94%
	Guselkumab	60	50%		
3	Placebo	60	20%	35%	98%
	Guselkumab	60	55%		
4	Placebo	60	25%	25%	82%
	Guselkumab	60	50%		
5	Placebo	60	25%	30%	93%
	Guselkumab	60	55%		
6	Placebo	60	25%	35%	98%
	Guselkumab	60	60%		

HiSCR=Hidradenitis Suppurativa Clinical Response

1.5. Randomization and Blinding

1.5.1. Procedures for Randomization and Stratification

Central randomization will be implemented in this study. Participants will be randomly assigned to 1 of 3 intervention groups based on a computer-generated randomization schedule prepared under the supervision of the sponsor. Permuted block randomization with stratification by baseline weight (≤ 95 kg, > 95 kg) and baseline Hurley stage (I, II, and III) will be used. The number of participants in Hurley stage I should be limited to approximately 30% of the total planned number of participants. Additionally, the number of participants in Hurley stage III should be limited to approximately 50% of the total planned number of participants. The interactive web response system (IWRS) will assign a unique intervention code, which will dictate the intervention assignment and matching study intervention kits for the participant. The requestor must use his or her own user identification and personal identification number when contacting the IWRS, and will then be given the relevant participant details to uniquely identify the participant.

At Week 16, participants randomized to placebo at Week 0 will be rerandomized using the IWRS either to guselkumab 200 mg SC q4w or guselkumab 100 mg SC at Weeks 16, 20, and q8w thereafter (participants will receive placebo SC at Weeks 24 and 32) in a 1:1 ratio using permuted block randomization and the randomization and will be stratified by baseline weight (≤ 95 kg, > 95 kg) and baseline Hurley stage (I, II, and III).

1.5.2. Maintenance of Blind

The study blind will be maintained for the duration of the study, until after the Final (Week 48) DBL.

To maintain the study blind, the study intervention container will have a label containing the study name, study intervention number, and reference number. The blinded label will not identify the specific study intervention in the container (ie, guselkumab or placebo). However, if it is necessary for a participant's safety, the study blind may be broken and the identity of the study intervention ascertained. The study intervention number will be entered in the eCRF when the study intervention is administered. The guselkumab and placebo will be identical in appearance and will be packaged in identical containers.

The investigator will not be provided with randomization codes. The codes will be maintained within the IWRS, which has the functionality to allow the investigator to break the blind for an individual participant.

Data that may potentially unblind the intervention assignment (ie, study intervention serum concentrations, anti-guselkumab antibodies, and intervention allocation) will be handled with special care to ensure that the integrity of the blind is maintained and the potential for bias is minimized. This can include making special provisions, such as segregating the data in question from view by the investigators, clinical team, or others as appropriate until the time of DBL and unblinding.

Under normal circumstances, the blind should not be broken until all participants have completed the study and the database is finalized. However, selected sponsor personnel will be unblinded for analysis after the Week 16 DBL has occurred. All site personnel and participants will remain blinded to the treatment assignments until the last participant completes Week 48 evaluations and the database has been locked. The investigator may, in an emergency, determine the identity of the intervention by contacting the IWRS. While the responsibility to break the intervention code in emergency situations resides solely with the investigator, it is recommended that the investigator contact the sponsor or its designee if possible to discuss the particular situation, before breaking the blind. Telephone contact with the sponsor or its designee will be available 24 hours per day, 7 days per week. In the event the blind is broken, the sponsor must be informed as soon as possible. The date and reason for unblinding must be documented in the appropriate section of the eCRF, and in the source document. The documentation received from the IWRS indicating the code break must be retained with the participant's source documents in a secure manner.

Participants who have had their intervention assignment unblinded by the investigator will not be eligible to receive further study intervention, but should continue to complete evaluations specified in the Schedule of Activities (Section 1.3 of the protocol).

An independent, external DMC will monitor the safety of the study in an unblinded fashion on a regular basis and whenever deemed necessary. In addition, the Sponsor Medical Monitor will review safety data in a blinded manner as the study is ongoing. The DMC's roles and responsibilities, the safety data for DMC review, and other related information (such as, the general procedures, communications, etc.) are defined and documented in the DMC charter.

In addition, an internal Sponsor Interim Analysis Committee and the statistical supporting group (SSG) otherwise not involved in the study conduct will have access to the unblinded data when approximately 30% of the participants have completed their Week 16 visit or have terminated their study participation before Week 16

For the planned interim analyses and the DMC review, the randomization codes and the translation of randomization codes into intervention and control groups will be disclosed to those authorized.

2. GENERAL ANALYSIS DEFINITIONS

This analysis plan provides the general analysis definitions and describes the planned subject information, efficacy, safety, pharmacokinetics, and antibody analyses for the two planned DBLs.

2.1. Imputation Rules for Partial or Missing AE Dates

Partial AE onset dates will be imputed as follows:

- If the onset date of an adverse event is missing day only, it will be set to:
 - First day of the month that the AE occurred, if month/year of the onset of AE is different than the month/year of the study agent start
 - The day of study agent start, if the month/year of the onset of AE is the same as month/year of the study agent start date and month/year of the AE resolution date is different
 - The day of study agent start or day of AE resolution date, whichever is the earliest, if month/year of the onset of AE and month/year of the study agent start date and month/year of the AE resolution date are same
- If the onset date of an adverse event is missing both day and month, it will be set to the earliest of:
 - January 1 of the year of onset, as long as this date is on or after the study agent start date
 - Month and day of the study agent start date, if this date is in the same year that the AE occurred
 - Last day of the year if the year of the AE onset is prior to the year of the study agent start date,
 - The AE resolution date.
- Completely missing onset dates will not be imputed.

Partial AE resolution dates not marked as ongoing will be imputed as follows:

- If the resolution date of an adverse event is missing day only, it will be set to the earliest of the last day of the month of occurrence of resolution or the date of death, if the death occurred in that month.
- If the resolution date of an adverse event is missing both day and month, it will be set to the earliest of December 31 of the year or the day and month of the date of death, if the death occurred in that year.
- Completely missing resolution dates will not be imputed.

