4.4. Extent of Exposure

The exposure data through Week 16 and through Week 36 will be summarized. The number and percentage of participants who receive study agent will be summarized by treatment group for the safety analysis set. Descriptive statistics will be presented for the following parameters:

- Number of administrations
- Cumulative total dose

Study agent lots received by treatment, including matching placebo for active treatment will be summarized.

In addition, the average exposure (number of administrations) and average duration of follow-up (weeks) will also be summarized by treatment group in the safety tables through different study time periods.

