6. SAFETY

Safety will be assessed by summarizing the incidence and type of AEs and examining changes in laboratory parameters (hematology and chemistry), vital signs, and suicidal ideation and behavior as measured by the C-SSRS (Columbia-Suicide Severity Rating Scale).

In all the safety analysis, randomized participants who received at least 1 (partial or complete) dose of study agent administration will be included and analyzed according to the treatment they actually received, regardless of the treatments they are randomized to. No formal statistical comparison is planned.

Depending on the safety data categories, the cumulative safety data will be analyzed through different study periods through Week 16 and Week 48. Unless otherwise specified, tabular summaries of safety events for key study periods are in general presented as following:

Summaries through Week 16 (placebo controlled):

Safety data through Week 16 will be summarized by treatment groups

1. Placebo
2. Guselkumab 200 mg SC
3. Guselkumab 1200 mg IV
4. Combined Guselkumab

This allows between-group comparisons of safety between the guselkumab regimens and the placebo group based on similar follow-up period in each group.

Summaries through Week 48

Safety data through Week 48 will be summarized by treatment groups including

1. Placebo → guselkumab 100 mg SC
2. Placebo → guselkumab 200 mg SC
3. Guselkumab 200 mg SC
4. Guselkumab 1200 mg IV
5. Combined Guselkumab

This allows safety comparisons between each guselkumab regimen through Week 48 based on the similar follow-up time in each group.

The list of actual treatment groups for safety analyses and inclusions of participants and safety events/measurements in each group are defined as follows:

1. **Placebo:** all participants who were randomized to placebo at Week 0 and received treatment with placebo only or received treatment with placebo prior to receiving treatment with guselkumab. For participants who started treatment with placebo but later received

guselkumab, the safety events/measurements on and after the first dose of guselkumab will be excluded from this group. Only the safety events/measurements that occurred while the participants had been receiving placebo only will be included in this group.

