2. **Placebo → guselkumab 100 mg SC:** all participants who were randomized to placebo at Week 0 started treatment with placebo only and later randomized to treatment with guselkumab 100 mg SC q8w. Only the safety events/measurements from these participants that occurred on and after their first administration of guselkumab will be included in this group.
3. **Placebo → guselkumab 200 mg SC:** all participants who were randomized to placebo at Week 0 started treatment with placebo only and later randomized to treatment with guselkumab 200 mg SC q4w. Only the safety events/measurements from these participants that occurred on and after their first administration of guselkumab will be included in this group.
4. **Guselkumab 200 mg SC:** all participants who were randomized to guselkumab 200 mg SC q4w at Week 0 and received guselkumab. All the safety events/measurements from these participants that occurred from Week 0 will be included in this group.
5. **Guselkumab 1200 mg IV:** all participants who were randomized to guselkumab 1200 mg IV q4w at Week 0 and received guselkumab. All the safety events/measurements from these participants that occurred from Week 0 will be included in this group.

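### Partial adverse-event dates are imputed only against first study agent, so some events that began after the Week 16 crossover drop out of the guselkumab safety columns through Week 48

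*SAP*

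**What the plan says.** SAP 2.1 imputes partial onset dates against two anchors only, the start of study agent and the resolution date of the event.

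- **Day missing, month differs from the start month:** "First day of the month that the AE occurred, if month/year of the onset of AE is different" from the study agent start.
- **Day missing, month equals the start month:** "The day of study agent start, if the month/year of the onset of AE is the same as month/year of the study agent start date", with the resolution date used instead when it falls in the same month and is earlier.
- **Day and month missing:** the earliest of several candidates, among them "January 1 of the year of onset, as long as this date is on or after the study agent start date".
- **Nothing known:** "Completely missing onset dates will not be imputed".

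Study agent includes placebo. SAP 4.4 says "Study agent lots received by treatment, including matching placebo for active treatment will be summarized". The start date for a placebo participant is therefore the Week 0 placebo dose.

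SAP 1.2 has placebo participants cross over later: "At Week 16, participants will be rerandomized in a 1:1 ratio to either guselkumab 200 mg SC q4w through Week 36", or to the 100 mg regimen. SAP 6 then splits their safety data at that second start. For the placebo group, "the safety events/measurements on and after the first dose of guselkumab will be excluded from this group". For each placebo-to-guselkumab group, "Only the safety events/measurements from these participants that occurred on and after their first administration of guselkumab will be included in this group". The table through Week 48 lists the two crossover groups, the two groups on guselkumab from Week 0, and Combined Guselkumab. It has no placebo column.

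SAP 6.1 decides only whether an event is treatment emergent relative to the initial dose of study agent. It does not allocate events between placebo and guselkumab.

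**The concern.** The imputation rule and the attribution rule use different dates. SAP 2.1 is careful at the first start: an ambiguous onset in the start month is placed on the start day, so it is not lost as pre-treatment. SAP 6.1 takes the same cautious line and treats a partially dated event as treatment emergent unless it is known to be earlier. Neither safeguard is repeated at first guselkumab, which for these participants is the first exposure to the active drug.

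Within the crossover participants the error runs one way. Day 1 of a month is never later than the true onset in that month, so an event can move from guselkumab to placebo but not the reverse. Because the Week 48 table has no placebo column, a moved event leaves that table altogether. It leaves the Combined Guselkumab column too, if that column pools the four groups listed above it, as I assume. This is not only a missing detail: the rule as written gives a definite answer, and for these events the answer is wrong.

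**Working it through.** The plan states no figure on this point, so there is none to reproduce. The check applies the written rules to dates.

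**Inputs from the documents.** Crossover is at Week 16 (SAP 1.2), day +112 from first dose. The visit window is ±7 days (SAP 2.2), giving day +105 to +119. The planned placebo group is 60 (SAP 1.4), re-randomised 1:1, so 30 per crossover column.

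**Assumptions.** True onset is uniform over the days of the crossover month. The calendar runs over every first-dose date in 2018 to 2021 (1461 dates, an arbitrary choice).

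1. **Which branch applies.** Crossover comes at least 105 days after first dose and no month exceeds 31 days, so the crossover month is never the start month (0 of 1461 dates). The first-of-month branch always governs.

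2. **How often day 1 precedes first guselkumab.** It does so unless crossover is itself on the 1st: 96.7% of start dates, the same at +105, +112 and +119.

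3. **How many of these events are wrongly placed.** On average 51.6% of the days in the crossover month fall on or after first guselkumab, and 93.6% of those days would be charged to placebo. The product is 0.516 × 0.936 = 0.48. So about 48% of all day-missing onsets in that month are misassigned. A further 1 − 0.516 = 0.48 truly began before crossover and are correctly counted as placebo.

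4. **Example.** First dose 5 March 2019, crossover 25 June 2019 (day +112). An event dated only June 2019 is imputed to 1 June and counted before guselkumab, even if it began on 28 June.

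5. **Expected number.** The documents give neither event rates nor the frequency of partial dates. Assume 0.3 to 0.5 events per participant-month and 2 to 5% with the day missing.
   - Ambiguous events: 60 × 0.3 × 0.02 = 0.36, up to 60 × 0.5 × 0.05 = 1.5.
   - Truly misassigned: 0.36 × 0.48 = 0.17, up to 1.5 × 0.48 = 0.72.

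6. **Weight of one event.** One participant is 1/30 = 3.3 percentage points in a crossover column and 1/180 = 0.6 points in Combined Guselkumab, if all 60 cross over and the column pools all 180 planned participants.

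7. **Year-only dates.** When the onset year is the crossover year, the imputed date precedes crossover for 99.7% of start dates. Many such events may truly have begun on placebo, so this figure is not a misassignment rate.

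**The case against.** A reader might infer that the rule flatters guselkumab in the comparison with placebo. The documents do not support that. The first-of-month rule applies to every participant. In the two arms on guselkumab from Week 0, a day-missing onset that truly fell just after Week 16 is also moved to day 1, and so into the through-Week-16 table. If that table is cut at the Week 16 visit in those arms, all three columns are shifted alike per participant. SAP 6 presents this table as the between-group comparison with placebo, and it is not clearly biased. This part of the objection stands and confines the problem to the Week 48 columns.

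It also limits the remedy. Moving ambiguous events to guselkumab for placebo participants alone in the Week 16 table would deflate placebo and leave the guselkumab arms unchanged, creating an asymmetry in the one randomised safety comparison.

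Four further points stand:

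- Events that truly began before crossover are rightly placed, so only about half of the ambiguous ones count.
- Completely missing onset dates are not imputed and lie outside this point.
- Serious events are reported within 24 hours of site knowledge (Protocol 8.3.1) and eCRF entries are queried, so a serious event with no onset day should be uncommon. The 3.3-point figure is an upper-end illustration.
- SAP 6 plans no formal statistical comparison of safety, so no test depends on the split.

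None of this restores the events lost from the Week 48 columns.

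**Conclusion.** The point holds for the placebo-to-guselkumab and Combined Guselkumab columns through Week 48. A day-missing onset in the crossover month is counted before guselkumab whenever crossover is not on the 1st, and no other section corrects it. The expected loss is small: about 0.2 to 0.7 events out of 0.4 to 1.5 ambiguous ones. This rests on 60 participants crossing over, uniform onset within the month, and the assumed event and missing-day rates. Any dropout before Week 16 lowers it. Efficacy analyses are not affected. It is a minor defect, worth correcting because the columns concerned describe first exposure to guselkumab and the correction is cheap.

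**What to change.** Add one sentence to SAP 2.1, referenced from SAP 6: for participants randomised to placebo who cross over, when the day of onset is missing and the onset month and year equal those of first guselkumab, impute the date of first guselkumab, or the resolution date if earlier, for assigning events to the placebo-to-guselkumab and Combined Guselkumab columns through Week 48. State that the through-Week-16 table keeps one imputation rule for all three arms.

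Do not add a parallel rule sending year-only dates to guselkumab. It would charge the active drug with events from what may be several months on placebo in that year.

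There are two costs. Some events that truly began on placebo in the crossover month will be charged to guselkumab unless their resolution date shows otherwise. That is the conservative direction and the trade-off SAP 2.1 already accepts at first study agent. Also, the same ambiguous event could appear under placebo in the Week 16 table and under guselkumab in the Week 48 table, so a footnote giving the number of such events is advisable. No new data collection is needed.
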